10.3 Statistical Considerations

10.3.1 General Considerations

Continuous data will be summarized using the number of observations, mean, 95% confidence interval of the mean (unless specified otherwise), standard deviation, median, 25% (Q1) and 75% (Q3) percentiles, minimum and maximum.

PREOB-ON3 - Clinical Study Protocol

PREOB-ON3-CSP	V 6.1	Author: [name]	May 15, 2017	Pg. 86/87
---------------	-------	----------------	--------------	-----------

Categorical data will be presented in contingency tables along with number of patients, percentages and their 95% confidence interval (unless specified otherwise).

Statistical tests will be two-sided at 5% significance level. Adjustment to control the type I error for multiplicity will be performed as described in Section 10.7 on interim analysis. Except for the adjustment made for the interim analysis, no additional adjustments for multiple comparisons will be done in this study.

AEs, SAEs and medical history terms will be coded using the most recent version of the Medical Dictionary for Regulatory Activities (MedDRA). Concomitant medications will be coded using the most recent version of the WHO drug dictionary.

Statistical analyses will be performed using the SAS® software (SAS Institute, Cary, NC, USA) version 9.2 or higher.

The Final Clinical Study Report will be established based on the efficacy and safety data collected up to 24 months. The long-term follow-up data (collected at 36 and 48 months after IMP implantation) will be analysed and reported as Annexes and Supplementary Data to the Final Clinical Study Report.

10.3.2 Statistical Hypotheses for the Primary Endpoint

The superiority of PREOB® over Placebo will be considered achieved if the percentage of treatment responders is statistically significantly higher in the PREOB® group than in the Placebo group at Month 24 (primary endpoint).

- H0 (null hypothesis): the difference in percentages between PREOB® and Placebo is equal to 0,
- H1 (alternative two-sided hypothesis): the difference in percentages between PREOB® and Placebo is different from 0 (with percentage PREOB® \geq percentage Placebo).

Superiority will be proven if the *p*-value of the statistical test comparing the percentages of treatment responders between PREOB® and Placebo is less than or equal to the Type I error (two-sided) as defined in Section 10.7 in which case the null hypothesis H0 will be rejected in favor of the alternative hypothesis H1.

10.4 Sample Size

The single sample size test is planned with a two-sided 5% significance level and a power of 90% assuming the use of Chi-square test (see Table 14). The proportion of treatment responders

PREOB-ON3 - Clinical Study Protocol

PREOB-ON3-CSP V 6.1 Author: [name] May 15, 2017 Pg. 87/88

is assumed to be equal to 63% for the PREOB® group and 30% for the Placebo group. These hypotheses have been estimated on the basis of the Phase IIb data set.

Table 14: Sample size estimation - Chi-square test

Test?	Chi-square
Test significance level, α	0.05
1 or 2-sided test?	2
Group 1, PREOB® proportion, π_1	0.63
Group 2, Placebo proportion, π_2	0.30
Power (%)	90
N per arm	46

A Chi-square test with a 5% two-sided significance level will have 90% power to detect the difference between a Group 1 proportion, π_1 , of 0.63 and a Group 2 proportion, π_2 , of 0.30 when the overall sample size is 92 patients (46 patients in the PREOB® group and 46 patients in the Placebo group).

As an interim analysis is planned in the study using a group sequential design approach, the maximum sample size must be increased to achieve the desired power of 90% at final analysis. The increase in sample size depends on the overall significance level, the statistical power, the number of interim analyses and the type of boundaries being used (See section 10.7). Thus, the maximum sample size is obtained by multiplying the above fixed sample size by a constant determined by these parameters. For the current study, the maximum sample size is 110 patients (1.19 * 92 patients).

Taking into account a drop out and lost to follow-up rate of 7.5%, the overall sample size should be of 118 patients (59 patients in the PREOB® group and 59 patients in the Placebo group) to ensure around 110 evaluable patients at Month 24.

Sample size was computed using the procedure seqdesign of SAS® software version 9.2.

Additional considerations for sample size estimation

Although no claim is intended for the comparison of efficacy endpoints other than the primary endpoint, sample size calculations have been conducted to ensure that such comparisons may be performed with sufficient power to provide additional characterization of the treatment effect and yield supportive evidence related to the primary objective.

PREOB-ON3 - Clinical Study Protocol

PREOB-ON3-CSP

V 6.1

Author: [name]

May 15, 2017

Pg. 88/89

10.5 Analysis Sets

Three different sets of population will be used in the analysis of this study: a safety set (SAF), a full analysis set (FAS), and a per-protocol set (PP).

The safety set (SAF) will include all treated patients, *i.e.*, patients with both (i) core decompression and (ii) PREOB® or Placebo implantation. Analyses on the SAF will be performed according to the IMP actually received.

The full analysis set (FAS) consists in a modified Intention-To-Treat population and will include all randomised and treated patients, with a baseline value available of both the ARCO stage and the WOMAC® pain subscale score, and at least one post-baseline value available of both the ARCO stage and the WOMAC® pain subscale score. Analyses on the FAS will be performed according to the randomisation group regardless of the IMP actually received.

The per-protocol set (PP) will be a subset of the FAS including all randomised and treated patients who had no major protocol deviations during the study. Analyses on the PP will be performed if the PP differs by more than 10% from the FAS.

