3.4 Product Implantation (Visit 3, Day 0 and Day +1)**Day 0**

The patient will be admitted to the Clinic on Day 0. The following examinations and procedures will then be performed by the Investigator:

[REDACTED]

[REDACTED]

[REDACTED]

[REDACTED]

[REDACTED]

[REDACTED]

[REDACTED]

On the same day, the shipping box containing the Investigational Medicinal Product (PREOB® or Placebo) will be shipped by the Manufacturer to the Pharmacy Department of the Investigating Site.

If the IMP is not useable due to a technical problem that occurred during the production process, the Managing Physician will immediately notify the CAs and SSO, and record relevant information in the eCRF. Once completed, the eCRF will automatically send e-mail alerts to the Study Safety Officer (SSO), and PI.

In case the IMP is not available for the implantation, the PI will inform the patient about the cancellation of the latter procedure. In this case, the patient will be considered as drop out, but the Investigator is however allowed to re-include the patient after 2 months (novel inclusion procedure).

Upon IMP receipt the Pharmacist will check if all the conditions listed on the Release Form for the Hospital - Hospital Pharmacist Section - are met, and subsequently release the IMP and immediately inform the Principal Investigator (and/or delegate) (see detailed description of related procedures in the SPM for Pharmacist). If released by the pharmacist, the IMP will be transferred to the Operating Room.

PREOB-ON3 - Clinical Study Protocol

PREOB-ON3-CSP

V 6.1

Author: [name]

May 15, 2017

Pg. 50/51

In the Operating Room, the Principal investigator will check if all the conditions listed on the Release Form for the Hospital - Principal Investigator Section - are met, and subsequently release the IMP and perform the surgical procedure (core decompression and implantation, PREOB® or Placebo) (see detailed procedures in Section 4.2 and in the SPM for PI).

After implantation, the empty PREOB® or Placebo syringe will be kept and stored by the Investigator (or a member of the investigating team designated by the Investigator) until the next Monitoring visit.

Day +1

Patients will be systematically evaluated 24 hours after the core decompression/implantation procedure, and will then be discharged from the Clinic after the following examinations:

[REDACTED]

[REDACTED]

[REDACTED]

[REDACTED]

[REDACTED]

[REDACTED]

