7 SAFETY: TOLERABILITY MEASUREMENTS AND ENDPOINTS

7.1 Overview of Safety Parameters and Endpoints

The treatment safety and tolerability will be systematically investigated throughout the study period. Patients will be evaluated at each follow-up visit for the potential occurrence of any AE or SAE, related to either the product or any study procedures (see Section 8 for Definitions of AE/SAE).

Table 8 below shows how the safety endpoints of this study relate to the study objectives. Assessments and measurements will be carried out at the timepoints specified in the main study schedule of visits and procedures (Table 2).

Table 8: Overview of Safety Parameters and Endpoints

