10.6.4 Safety Endpoint Analyses

Detailed statistical methodology for the safety analyses will be provided in the SAP.

Safety variables include AEs, SAEs, vital signs, physical examination, laboratory tests and concomitant medications. All safety analyses will be described by treatment group actually received and overall on the SAF. No replacement of missing safety data will be performed.

For each AE reported, the number and percentage of patients will be tabulated based on the MedDRA system organ class and preferred term. Similar tabulations will be performed by

PREOB-ON3 - Clinical Study Protocol

PREOB-ON3-CSP	V 6.1	Author: [name]	May 15, 2017	Pg. 90/91
---------------	-------	----------------	--------------	-----------

relationship to treatment and by severity. AEs will be distinguished between treatment-emergent AEs and non-emergent AEs (*i.e.*, AEs pre-implantation and AEs post-implantation).

Standard summary statistics of clinical and laboratory values, as well as shift tables presenting incidence of physical and laboratory abnormalities will also be provided by treatment group.

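### The safety set begins at implantation, so patients given the real or sham marrow harvest but never implanted fall outside every planned safety-set analysis

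*Combined protocol and SAP*

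**What the plan says.** Section 10.5 opens with "The safety set (SAF) will include all treated patients" and specifies them as "patients with both (i) core decompression and (ii) PREOB® or Placebo implantation". It adds "Analyses on the SAF will be performed according to the IMP actually received". The other two sets, FAS and PP, are also limited to treated patients.

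Section 10.6.4 places the whole safety analysis on this set: "All safety analyses will be described by treatment group actually received and overall on the SAF". It continues "AEs will be distinguished between treatment-emergent AEs and non-emergent AEs" and explains the split in a parenthesis as "AEs pre-implantation and AEs post-implantation".

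The Definitions list describes a drop out as someone randomised who never received treatment. Sections 3.4 and 4.2.1 apply the label to a patient whose product is unavailable on the day of implantation: "In this case, the patient will be considered as drop out". Both sections allow such a patient to be included again after two months.

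Randomisation (Section 3.2) precedes Visit 2, when the harvest is done at least 21 days before implantation (Sections 2.3.5 and 3.3). PREOB patients have a 50 ml marrow aspiration. Controls have local anaesthesia, a 5-mm incision and needle contact with the bone without entering it (Section 4.1).

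**The concern.** The treatment strategies separate at the harvest, not at implantation. From Visit 2, one arm has had marrow aspirated through the iliac crest and the other has had a shallower sham. A safety set that opens only once the implant is in place leaves out anyone who had that procedure and did not reach the implant. Grouping by product received could not place such a patient in any case, because no product was received.

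Section 7.1 says that patients will be evaluated for events "related to either the product or any study procedures", Section 8.2 asks for causality to be judged against the marrow harvest, and Section 10.2 counts adverse events over the whole study period. The plan therefore collects information on harvest harms, but its analysis set does not carry all of it. At stake is a complete account, by arm, of the harms of the harvest in a pivotal trial of 59 patients per arm, where each patient is 1.7% of an arm.

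**Working it through.** **Inputs.** From Section 10.4: assumed response rates 0.63 and 0.30, two-sided alpha 0.05, power 90%, 46 per arm, group-sequential factor 1.19, 110 evaluable patients, 7.5% drop out and loss to follow-up combined, 118 randomised (59 per arm). From Sections 10.5, 10.6.4, 3.4 and 4.2.1: the definitions set out above.

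**Step 1: the plan's own figures.** With mean rate (0.63 + 0.30)/2 = 0.465,

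n per arm = [1.960 × √(2 × 0.465 × 0.535) + 1.2816 × √(0.63 × 0.37 + 0.30 × 0.70)]² / 0.33² = (1.3825 + 0.8531)² / 0.1089 = 45.9, so 46, as stated (power 0.9007).

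Then 1.19 × 92 = 109.48, rounded to 110. Allowing for losses, 110/0.925 = 118.9, against the stated 118; 118 × 0.925 = 109.15, in line with the plan's aim of around 110. The base of 118 and the 7.5% allowance can be used below.

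**Step 2: follow one patient.** Randomised, harvested (real or sham), product not released on Day 0. Under Section 3.4 the patient is a drop out. Section 10.5 requires core decompression and implantation, so the patient is not in the safety set, nor in the FAS or PP. Section 10.6.4 names no other safety population, so the patient appears in no planned safety-set analysis. The same holds for any patient who withdraws between Visit 2 and Visit 3.

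**Step 3: follow one event.** An implanted patient has a haematoma at the harvest site. It starts before implantation. Read in order, the parenthesis in Section 10.6.4 would make pre-implantation events the emergent ones, so the two classes are listed in reverse. The Table 13 footnote, on the Phase IIb study, counts events on or after the implantation date as emergent, which shows the intended direction. The haematoma is therefore kept, by group, as non-emergent.

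**Step 4: size.** The number harvested but not implanted is not given. The plan's combined allowance is 118 × 0.075 = 8.85, about 9 patients, if every loss were a non-implanted drop out. It also covers loss during the 24 months after implantation, so the non-implanted share is an unknown part of it. Assumed counts:

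| Harvested, not implanted | Share of 118 | Share of 59, if all were in the PREOB arm (assumption) |
|---|---|---|
| 1 | 0.8% | 1.7% |
| 3 | 2.5% | 5.1% |
| 5 | 4.2% | 8.5% |
| 9 | 7.6% | 15.3% |

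As an extreme illustration: if three PREOB patients were not implanted, each had a given harvest event and nobody else in the arm did, the safety set would show 0 of 56, while all harvested PREOB patients would show 3 of 59 (5.1%).

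**Step 5: direction.** Marrow is cultured only for PREOB (Section 4.1), and the placebo contains no cells (Table 5), so culture failure can arise in one arm only. The pharmacist's and the investigator's release checks (Sections 3.4 and 4.2.1) and the withdrawal reasons in Section 9.1 apply to both arms. The documents give no count by arm.

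**The case against.** The strongest reply is that little is lost. Adverse events are collected from screening (Table 11). Section 8.3.1.2 requires every serious event from screening onward to be reported within 24 hours, Section 8.3.2 covers them in annual reports, the monitoring board sees safety data, and the study report includes individual listings. Table 12 lists only site pain and local haematoma for the harvest, with no serious event. The cut at implantation is the same in both arms and follows the Phase IIb convention. Section 10.6.4 leaves detail to the SAP, and the document supplied contains no separate SAP text, so a harvest table there cannot be excluded. Section 7.1 describes what is evaluated at follow-up visits; it is not the study objective.

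Most of this stands, and it rules out three stronger conclusions that a reader might draw:

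- **That harvest harms vanish.** They do not. Implanted patients' events remain in a separate class, and excluded patients' serious events are still notified.
- **That few or no placebo patients would be lost.** No figure supports this, and several routes to non-implantation apply to both arms. A patient included again could also enter the safety set later.
- **That the comparison favours PREOB.** This is a possible direction, not a demonstrated effect.

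The reply does not answer the core point. Individual notification and listings are not a tabulation by arm, and the protocol sends all safety analyses to a set that these patients cannot enter. Nor is collection fully secured: Section 8.2.1 makes the observation periods binding for treated patients only.

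**Conclusion.** The point holds. As the protocol is written, patients who had the real or sham harvest but no implant are outside every planned safety-set analysis, and the by-arm account of harvest harms is incomplete. In implanted patients the matter is one of classification: harvest-period events are retained as non-emergent, and the wording that defines the two classes is in reverse order.

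The size is unknown. Taking the plan's 7.5% as correct and every loss as a non-implanted drop out gives about 9 of 118; the actual share of that allowance is not stated. Unequal loss is plausible because of culture failure, so the safety comparison can be tilted, but the documents do not show that it is. Sample size and efficacy analyses are unaffected. The conclusion about tables rests on the protocol text and would need revisiting if a separate SAP already tabulates the harvest period for all harvested patients.

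**What to change.** In Sections 10.5 and 10.6.4 and in the SAP:

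1. Add a safety set of all randomised patients in whom the real or sham harvest was started, grouped by the procedure actually received.
2. On that set, tabulate adverse events by arm in two separate periods: from the start of the harvest to implantation (or to the end of observation if there is none), and after implantation.
3. Keep the implanted patients as the set for product-related, treatment-emergent tables, so that comparison with the Phase IIb convention is preserved.
4. Correct the order of the parenthesis so that non-emergent corresponds to pre-implantation and emergent to post-implantation.
5. State in Section 8.2.1 that adverse events of harvested but non-implanted patients are collected, and for how long. For patients included again, state how events from the first harvest are counted.
6. Report by arm the number harvested but not implanted, with reasons.

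The cost is one extra set of tables, the wording changes, and a short collection rule for non-implanted patients. The rule is needed because the observation periods now bind only for treated patients. Adverse-event recording already starts at screening, and no sample-size figure changes.

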The full analysis set (FAS) consists in an modified Intention-To-Treat population and will be considered as the primary cohort for analysis of efficacy.

The superiority of PREOB® over Placebo will be considered achieved if the percentage of treatment responders is statistically significantly higher in the PREOB® group than in the Placebo group at Month 24. The primary efficacy endpoint will be compared between the two groups by means of a Chi square or a Fisher's exact test (as appropriate). The difference between the two groups will be considered significant if the *p*-value is less than or equal to the Type I error.

Comparison between treatment groups of the secondary binary efficacy endpoints will be performed at each studied timepoint, by means of a Chi square test or a Fisher's exact test (as appropriate). Treatment effect over the 24-month follow-up period will be assessed using a Generalized Estimating Equations (GEE) model taking into account correlations between the repeated measurements within patients.

Comparisons between treatment groups of the secondary continuous efficacy endpoints will be performed at each studied timepoint by means of a parametric Student t-test or a non-parametric Wilcoxon rank-sum test (as

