8.4 Procedure in Case of Pregnancy

Women included in the study must be post-menopausal (defined as at least 12 months post cessation of menses), surgically sterile or, for women with childbearing potential, using a reliable method of contraception for at least 6 weeks prior to study entry (Screening Period, Visit 1) and during the whole study period. Women with childbearing potential will undergo pregnancy tests at all study visits, and at the last visit to the clinic in case of premature discontinuation. However, if a female patient becomes pregnant during the trial, she will be followed as per study procedure but will **NOT** undergo bilateral X-ray and MRI of the hip.

Any pregnancy will be systematically followed and reported within 24 hours of diagnosis to the Study Safety Officer and Monitor (Pregnancy Form will be immediately completed in the eCRF, with subsequent urgent notification), and their outcomes will be reported to the Study Safety Officer and Monitor.

Any pregnancy will be handled as an SAE regardless the relationship between the Investigational Medicinal Product and the event. Any complication arising during pregnancy will be recorded as an AE and will constitute a SAE if it fulfils any of the specified criteria for a SAE.

At the end of the pregnancy, whether that be full-term or premature, information on the status of the mother and child will be forwarded to Study Safety Officer.

If the outcome of pregnancy is:

- Elective abortions without complications, they will be recorded, documented and reported to the Study Safety Officer and Monitor, but they should not be handled as AEs;
- Any spontaneous miscarriages or abortions for medical reasons, or congenital abnormalities or birth defects, will be recorded, documented, reported, and handled as SAEs and full details will be requested.

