9.2 Procedure for Early Discontinuation

In case of early discontinuation and whenever possible, Investigators will ask patients to perform Visit 9 (Exit Visit) as the Premature Discontinuation Visit. At the end of the Exit visit, the Investigator will declare early discontinuation in the eCRF. However, the Investigator will continue to follow the patient (via phone calls) for the occurrence of any AEs and SAEs at Month 24, 36 and 48 post-treatment (See Table 11).

All collected data, during the visits and phone calls, should be recorded in the source documents and eCRF.

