10.1.2 Secondary Efficacy Endpoints

Efficacy will be assessed by the following secondary endpoints:

- Percentage of treatment responders at Month 6, 12 and 18, and over the 24-month follow-up period
- Percentage of clinical responders at Month 1, 3, 6, 12, 18 and 24, and over the 24-month follow-up period; a clinical responder being defined as a patient whom the WOMAC® VA3.1 pain subscale score of the study treated hip improved from baseline by at least the MCID^b at the studied timepoint
- Percentage of radiological responders at Month 6, 12, 18 and 24, and over the 24-month follow-up period; a radiological responder being defined as a patient whom the study treated hip did not progress to fractural stages (ARCO III or higher), as assessed by conventional X-ray, at the studied timepoint
- Absolute change from baseline in WOMAC® VA3.1 total score and composite pain, stiffness, and function subscale scores of the study treated hip at Month 1, 3, 6, 12, 18 and 24, and over the 24-month follow-up period
- Time to progression to fractural stages (ARCO III or higher) of the study treated hip
- Percentage of patients requiring hip arthroplasty for the study treated hip at Month 1, 3, 6, 12, 18 and 24, and over the 24-month follow-up period
- Time to hip arthroplasty for the study treated hip

^b The MCID value is set at 10 mm.

Patients with a baseline WOMAC® VA3.1 pain subscale score ≥ 10 mm will be considered, at the studied timepoint, as a clinical responder if the WOMAC® VA3.1 pain subscale score of the study treated hip decreased from baseline by at least the MCID.

Patients with a baseline WOMAC® VA3.1 pain subscale score < 10 mm will be considered, at the studied timepoint, as a clinical responder if the WOMAC® VA3.1 pain subscale score of the study treated hip is found in the range [0;4] (VAS pain range labelled as “no pain”).

PREOB-ON3 - Clinical Study Protocol

PREOB-ON3-CSP

V 6.1

Author: [name]

May 15, 2017

Pg. 85/86

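### The FAS requires a post-baseline ARCO stage, so treated patients who leave before Month 6 without any exit or unscheduled image are removed from the primary analysis

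*Combined protocol and SAP*

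**What the plan says.** The synopsis (Efficacy Analysis) states that the FAS "will be considered as the primary cohort for analysis of efficacy" and describes it as a modified intention-to-treat population. Section 10.5 sets three conditions: the patient was randomised and treated, has baseline ARCO stage and WOMAC pain, and has "at least one post-baseline value available of both the ARCO stage and the WOMAC® pain subscale score".

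Section 10.1.2 gives different starting points for the two components: "Percentage of clinical responders at Month 1, 3, 6, 12, 18 and 24" but "Percentage of radiological responders at Month 6, 12, 18 and 24, and over the 24-month follow-up period". Treatment response, which needs both components, is also listed from Month 6.

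Four other sections bear on who ends up with an image:

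- Section 3.5 says an exit visit will be completed when a treated patient discontinues, with Month 24 contact by phone.
- Section 9.2 is softer: where possible, "Investigators will ask patients to perform Visit 9 (Exit Visit) as the Premature Discontinuation Visit".
- Section 9.1 (reaching of endpoint) requires fracture to be documented by the central radiologist before discontinuation. Severe pain has to be documented by WOMAC only.
- Section 10.6.1 leaves the replacement of missing post-baseline data to the SAP, whose text is not in the documents supplied.

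**The concern.** Membership of the primary cohort depends on something that happens after randomisation and treatment: whether the patient was imaged again. The patients at risk of exclusion are those who die, are lost to follow-up, withdraw consent without an exit visit, or have the hip replaced for pain with no prior image, all before the first listed radiological time point. They may have pain scores at Months 1 and 3 and still fall outside the FAS.

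As 10.5 and 10.6.1 are written, replacement rules act on data of patients already in the analysis set. They cannot bring these patients back.

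The plan itself foresees early failure, since hip arthroplasty at Months 1 and 3 is a secondary endpoint. If such patients are mostly poor outcomes and leave one arm's denominator more often than the other's, the responder comparison is no longer the randomised one. The Month 1 and 3 clinical-responder analyses, if run on the FAS, would also lose patients for whom data exist.

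**Working it through.** **Inputs from the plan.** Responder rates 63% v 30%, 5% two-sided, 90% power, chi-square, 92 patients for the fixed design, factor 1.19, 7.5% loss, 118 in total (10.4). Final level 0.01341 per tail (10.7), so 2 × 0.01341 = 0.02682 two-sided.

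**Plan's own figure.** The pooled two-proportion formula without continuity correction gives 45.9, so 46 per arm (92 in total). Then 1.19 × 92 = 109.5, stated as 110. Finally 110/0.925 = 118.9, against the stated 118, and 118 × 0.925 = 109.2. The planned size is reproduced to within a patient.

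**Assumptions.** The documents give no number of treated patients without a post-baseline ARCO stage. I use 0 to 9 of 118, because 7.5% × 118 = 8.9. I take all 59 per arm as treated and all excluded patients as non-responders. The 9 is generous: the 7.5% covers losses to Month 24 and drop-outs, whom the Definitions section describes as randomised but never treated.

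**Near-threshold example, 6 PREOB v 2 placebo excluded.** Uncorrected chi-square, z = (p1 − p2)/√[p̄(1 − p̄)(1/n1 + 1/n2)]:

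- FAS: 28/53 v 18/57 = 52.8% v 31.6%, z = 0.2125/0.0941 = 2.26, p = 0.024, below 0.0268.
- All treated: 28/59 v 18/59 = 47.5% v 30.5%, z = 0.1695/0.0898 = 1.89, p = 0.059, not significant.

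**Opposite direction, 4 placebo failures excluded.** All treated: 31/59 v 19/59, p = 0.025. FAS: 31/59 v 19/55, p = 0.053. Here the exclusion hides a significant result.

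**Balanced exclusion, 4 v 4.** FAS: 31/55 v 19/55, p = 0.022. All treated: 31/59 v 19/59, p = 0.025. The conclusion is the same. Only a result on the boundary itself moves: 34/55 v 22/55, p = 0.0221, against 34/59 v 22/59, p = 0.0270. That is lost precision, not bias.

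**No true difference.** With 30% response in both treated arms (0.30 × 59 = 17.7 responders each), a 6 v 2 split gives 17.7/53 − 17.7/57 = 33.4% − 31.1% = +2.3 points. The upper-tail error becomes 0.026 instead of 0.0134. A 9 v 0 split gives +5.4 points and 0.054. A 4 v 4 split gives no difference and 0.0134.

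**Power when excluded patients are put back.** FAS rates are held at 63% v 30% and the excluded return as non-responders out of 59 per arm. Power = Φ[(d − 2.214·s0)/s1], with s0 the pooled and s1 the unpooled standard error, for a single test at the final level. For 4 v 4: FAS (0.33 − 2.214 × 0.0951)/0.0898 = 1.33, or 90.8%; all treated (0.3076 − 2.214 × 0.0912)/0.0867 = 1.22, or 88.8%.

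| Excluded, PREOB v placebo | Difference, all treated (points) | Power, FAS | Power, all treated |
|---|---|---|---|
| 0 v 0 | 33.0 | 92.8% | 92.8% |
| 4 v 4 | 30.8 | 90.8% | 88.8% |
| 6 v 2 | 27.6 | 90.8% | 80.2% |
| 2 v 6 | 33.9 | 90.8% | 94.4% |
| 9 v 0 | 23.4 | 90.4% | 64.5% |
| 0 v 9 | 37.6 | 90.3% | 98.0% |

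**The case against.** The strongest reply is that the plan has safeguards and the affected group may be very small.

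- A reader might infer that every patient who fails early leaves the FAS. The documents do not support that. A patient whose pain worsens but who stays reaches the Month 6 assessment. A fracture leading to discontinuation must first be centrally read. Section 3.5 says an exit visit will be completed, and Visit 9 is the Month 24 visit, at which the X-ray part of the primary endpoint is due.
- A reader might also infer that the plan counts missing patients as failures and that the FAS overrides this. No visible text says so. Section 10.1.1 defines response by pain and X-ray at the time point, so a lost patient's status is unknown.
- That no image is due before Month 6 is inferred from the endpoint list. Table 2 and the contents of Visits 4, 5 and 9 cannot be read, so the X-ray at Visit 9 is likewise an inference.
- Pregnancy is a weak example. Such a patient "will NOT undergo bilateral X-ray and MRI of the hip", but section 8.4 keeps her in follow-up and imaging time points continue to Month 24.
- The reversals need unequal exclusion and a near-threshold result. Starting from 31/59 v 19/59, losing a single placebo failure (31/59 v 19/58, p = 0.031) already crosses the line. At the planned rates, dropping four from one arm leaves the result clearly significant: 37/55 v 18/59, p < 0.0001; 37/59 v 18/55, p = 0.0014.
- Secondary p-values are exploratory (10.6.2), so the Month 1 and 3 consequence is minor.

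All of this stands, and it narrows the point. It does not remove it. Death, loss to follow-up or withdrawn consent can prevent an exit visit, section 9.2 asks for one only where possible, and arthroplasty for pain can occur with WOMAC documentation alone.

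**Conclusion.** The point holds in a limited form. Treated patients who leave before Month 6 with no exit or unscheduled image are excluded from the primary efficacy analysis on a post-randomisation event, whatever pain data they have.

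Its size cannot be stated, because the number of such patients is not in the documents. Balanced exclusion causes no bias under the null. Unequal exclusion does, in either direction: at an assumed 6 v 2 split with equal true response of 30%, the spurious difference is 2.3 points and the upper-tail error about doubles, from 0.013 to 0.026. A reader might conclude that the FAS favours PREOB; nothing in the plan fixes the direction.

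This rests on three assumptions: that the first scheduled image is at Month 6, that the excluded patients are non-responders, and that the SAP, which the protocol makes the main statistical reference, does not redefine the FAS. The correction should be made before database lock, because it needs only wording and removes an avoidable source of bias from a pivotal comparison.

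**What to change.** 1. In 10.5, delete the post-baseline condition, so that the FAS is all randomised and treated patients with baseline ARCO stage and WOMAC pain. Make the same change in the SAP if it repeats the condition.
2. State that a treated patient with no post-baseline ARCO stage is a non-responder at Month 24 in the primary analysis. Align this with the SAP rule for later missing Month 24 data, so that a patient lost at Month 5 and one lost at Month 7 are not treated on different principles.
3. For the Month 1 and 3 clinical endpoints, use every available WOMAC score at the visit.
4. Report by arm the number of treated patients with no post-baseline ARCO stage, with reasons.
5. Keep the current FAS as a sensitivity analysis.

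**Cost:** wording in the protocol and SAP before database lock, with no new data. Responder percentages fall slightly, and some power may be lost: about 88.8% against 90.8% for an assumed 4 v 4 split. The loss is larger if exclusions fall mainly in the PREOB arm (80.2% for 6 v 2), and power rises if they fall mainly in the placebo arm.
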